15.19 Nursing guidelines

15.191 Hypertension is very common with agent. Monitor BP as per protocol and report BP elevations to the study team.

15.192 Diarrhea is common. This may be increased in patients who are undergoing simultaneous treatment with immunotherapy agents. Instruct patients to report any diarrhea immediately and treat symptomatically per protocol instructions.

15.193 Other GI side effects can occur, including decreased appetite, weight loss, and nausea/vomiting. Manage patients symptomatically and monitor for effectiveness.

15.194 Patients may experience fatigue. Instruct patients in energy conserving lifestyle.

15.195 Dermatologic related side effects have been seen, including: hand-foot syndrome, rash, and alopecia. Instruct patients to report these signs and symptoms to the study team immediately.

15.196 Patients may experience increased risk of bleeding. Instruct patients to report any unusual bruising or bleeding to the study team. Patients should not undergo invasive procedures without first discussing with the study team.

15.197 Monitor for proteinuria per protocol.

15.198 Rarely agent may cause decreased LVEF. Instruct patients to report any peripheral edema, DOE, chest pain or significant fatigue to the study team.

15.199 Monitor LFT's and renal function. Report any elevations to the provider.

15.2 Pembrolizumab (Keytruda®)

Investigator brochure is available on the ACCRU web site.

- 15.21 **Background:** Pembrolizumab is a potent humanized IgG4 monoclonal antibody with high specificity of binding to the PD-1 receptor, thus inhibiting its interaction with PD-L1 and PD-L2. Based on preclinical *in vitro* data, pembrolizumab has high affinity and potent receptor blocking activity for PD-1.
- 15.22 **Formulation:** Pembrolizumab is available as a liquid 25 mg/mL, 100 mg/vial.
- 15.23 **Preparation and storage:** Vials should be stored in the refrigerator at temperatures between 2-8°C (36-46°F).

Drug concentrate is further diluted with normal saline (or 5% dextrose) in the concentration range of 1 to 10 mg/mL in IV containers made of polyvinyl chloride (PVC) or non-PVC material. The infusion solution in the IV bag should be immediately administered. Diluted pembrolizumab solutions may be stored at room temperature for a cumulative period of up to 4 hours. This includes room temperature storage of admixture solutions in the IV bags and the duration of infusion. The product can also be stored under refrigeration at 2°C to 8°C for no more than 96 hours from the time of dilution. If refrigerated, the diluted solution must be allowed to come to room temperature prior to administration. The solution must be discarded after 6 hours at room temperature or 96 hours under refrigeration.

- 15.24 **Administration:** Pembrolizumab is administered by intravenous infusion over 30 minutes via a 0.22 micron in-line filter. The final infusion volume must be between 1 and 10 mg/mL. Maximum rate of infusion should not exceed 6.7 mL/minute through a peripheral or indwelling catheter. Flush the line with 0.9% NaCl following the completion of the infusion.

15.25 **Pharmacokinetic information:**

a) Absorption – Because pembrolizumab is administered intravenously, it is immediately and completely bioavailable. Steady-state concentrations of pembrolizumab are reached by 16 weeks of repeated dosing with a Q3W regimen and the systemic accumulation is 2.1-fold. The peak concentration, trough concentration, and area under the plasma concentration versus time curve at steady state of pembrolizumab increased dose proportionally in the dose range of 2 to 10 mg/kg Q3W.

b) Distribution – Pembrolizumab has a limited volume of distribution.

c) Excretion – CL is approximately 23% lower after achieving maximal change at steady state compared with the first dose. The terminal elimination half-life ($t_{1/2}$) is estimated to be 22 days at steady state.

d) Metabolism - Pembrolizumab is catabolized through non-specific pathways; metabolism does not contribute to its CL.

There are no limited clinical studies on the subcutaneous formulation. Model-based analysis showed an estimated bioavailability of 64% (95% CI: 54% to 74%; variability, 128% CV). This is consistent with the reported bioavailability for other mAbs (range: 50% to 85%) given SC. Clearance was the same for the IV and SC formulations. The mean time to achieve maximum concentration (T_{max}) with pembrolizumab SC was

estimated to be 5.5 days (range: 3 days to 14 days).

15.26 **Potential Drug Interactions:** There are no known significant drug interactions.

15.27 **Known potential toxicities:**

Very common known potential toxicities, > 10%:

Gastrointestinal: diarrhea nausea

Skin and subcutaneous tissue disorders: rash, pruritus

General disorders and administration site conditions: fatigue

Common known potential toxicities, > 1% - 10%:

Blood and lymphatic system disorders: anemia

Immune system disorders: infusion related reaction

Endocrine disorders: Hypothyroidism, hyperthyroidism

Gastrointestinal disorders: colitis, vomiting, abdominal pain, constipation, dry mouth

Metabolism and nutrition disorders: decreased appetite

Musculoskeletal and connective tissue disorders: arthralgia, myositis, musculoskeletal pain, arthritis, pain in extremity

Nervous system disorders: headache, dizziness, dysgeusia

Respiratory thoracic, and mediastinal disorders: pneumonitis, dyspnea, cough

Skin and subcutaneous tissue disorders: severe skin reactions, vitiligo, dry skin, erythema

General disorders and administration site conditions: asthenia, edema, pyrexia, influenza like illness, chills

Investigations: alanine aminotransferase increased, aspartate aminotransferase increased, blood alkaline phosphatase increased, blood creatinine increased

Uncommon known potential toxicities, $\geq 0.1\%$ to $< 1\%$:

Cardiac disorders: myocarditis

Blood and lymphatic system disorders: neutropenia, thrombocytopenia, leukopenia, lymphopenia, eosinophilia

Eye disorders: uveitis, dry eye

Endocrine disorders: hypophysitis, adrenal insufficiency, thyroiditis

Gastrointestinal disorders: pancreatitis, dysphagia

Hepatobiliary disorders: hepatitis

Infusion related reactions

Metabolism and nutrition disorders: type I diabetes mellitus, hyponatremia, hypokalemia, hypocalcemia

Musculoskeletal and connective tissue disorders: tenosynovitis

Nervous system disorders: epilepsy, lethargy, peripheral neuropathy

Psychiatric disorders: insomnia

Renal and urinary disorders: nephritis, acute kidney injury

Skin and subcutaneous tissue disorders: lichenoid keratosis, psoriasis, alopecia, dermatitis, dermatitis acneiform, eczema, hair color changes, papule

Vascular disorders: hypertension

Investigations: blood bilirubin increased, amylase increased, hypercalcemia

Respiratory: aspiration pneumonia

Rare known potential toxicities, $< 0.1\%$ (Limited to important or life-threatening):

Blood and lymphatic system disorders: immune thrombocytopenic purpura,

hemolytic anemia

Immune system disorders: sarcoidosis

Nervous system disorders: Guillain-Barre syndrome, myasthenic syndrome

Gastrointestinal disorders: small intestinal perforation

Skin and subcutaneous tissue disorders: toxic epidermal necrolysis, Stevens-Johnson syndrome, erythema nodosum

The risk profile for pembrolizumab also includes two important potential risks: a) myasthenic syndrome, and b) an increased risk of severe complications (such as early severe graft versus host disease and veno-occlusive disease) of allogeneic transplant in patients with hematologic malignancies who have previously been treated with PD-1 inhibitors.

Patients with multiple myeloma who were treated with pembrolizumab in combination with either pomalidomide or lenalidomide and dexamethasone, had an increased number of serious side effects and deaths as compared to patients who received only dexamethasone and either pomalidomide or lenalidomide. The benefit-risk profile is unfavorable for the combination of pembrolizumab, pomalidomide, and dexamethasone in relapsed refractory multiple myeloma, and the combination of pembrolizumab, lenalidomide, and dexamethasone in newly diagnosed treatment-naive multiple myeloma.

- 15.28 Drug procurement: Investigational pembrolizumab is provided free of charge to patients by Merck. Each participating ACCRU membership will order a starter supply of pembrolizumab from Merck.

E-mail the Pembrolizumab Drug Order Request Form (found on the ACCRU web site) to:

Merck, Inc.

Each participating ACCRU treating location will be responsible for monitoring the supply of pembrolizumab and will use the Drug Order Request Form to order additional supplies as needed.

NOTE: in order to obtain a drug re-supply, Merck should be notified six months prior to study drug expiry.

Outdated or remaining drug is to be destroyed on-site as per procedures in place at each institution.

15.29 Nursing Guidelines:

15.291 Pembrolizumab side effects vary greatly from those of traditional chemotherapy and can vary in severity from mild to life threatening. Instruct patients to report any side effects to the study team immediately. Side effects may be immediate or delayed up to months after discontinuation of therapy. Most side effects are reversible with prompt intervention of corticosteroids.

- 15.292 Diarrhea can be seen, however, it is less common than what is seen with anti-CTLA-4 agents. It can occasionally be severe, leading to colonic perforation. Instruct patients to report ANY increase in the number of stools and/or change in baseline, blood in the stool, abdominal pain to the study team immediately.
- 15.293 Rash/pruritus/dermatitis is seen. Patients should report any rash to the study team. Treat per section 9.0 and monitor for effectiveness.
- 15.294 Monitor LFT's closely as elevations in these levels could indicate early onset autoimmune hepatitis. Patients should also be instructed to report any jaundice, or right upper quadrant pain to the study team immediately.
- 15.295 Pneumonitis can be seen and may be mild (only seen on imaging) to severe. Patients should be instructed to report any shortness of breath, dyspnea, cough, and/or chest pain to the study team immediately. Patients reporting these symptoms should have a pulse oximetry checked and consider immediate imaging per the treating physician.
- 15.296 Endocrinopathies (including hypopituitarism, hypothyroidism, hypophysitis, and adrenal insufficiency) are seen with this agent. Patients may present only with the vague sense of fatigue and "not feeling well." Additional symptoms may be that of nausea, sweating and decreased activity tolerance. Instruct patients to report these signs or symptoms immediately and obtain appropriate labs as ordered by the treating physician.
- 15.297 Patients who are started on steroid therapy for any side effects of pembrolizumab toxicity should be instructed to take the steroids as ordered, and not to discontinue abruptly as symptoms may return and be severe. Patients may be on steroid therapy for weeks. Instruct patients to report any increase or change in side effects with any dosage decrease as patients may need a slower taper.
- 15.298 Fatigue is common and may or may not be associated with immune-related side effects. Assess patient's fatigue level prior to each cycle of therapy and report any changes to the study team.
- 15.299a Patients should avoid receiving live vaccines within 30 days of study drug administration or per other study guidelines.
- 15.299b Patients who have undergone an allogenic bone marrow transplant, have an increased risk of severe complications including early GVHD, and veno-occlusive disease, if they have previously been treated with pembrolizumab.
- 15.299c Myocarditis has been reported and associated with pembrolizumab. Instruct patients to report chest pain, SOB, or dyspnea to study team immediately and/or seek emergency medical attention.
- 15.299d Autoimmune hematologic disorders including ITP and hemolytic

anemia have been reported. Monitor blood counts closely and report any abnormalities to the study team.

15.299e Rare neurologic disorders including Guillain-Barre syndrome and myasthenia gravis have been reported. Instruct patients to report any neurologic symptoms including weakness, paresthesia or numbness, tingling to the study team immediately.

16.0 Statistical Considerations and Methodology

16.1 Study Design/Endpoints

- 16.11 Background/Overview: This novel study will be the first to assess pembrolizumab and lenvatinib combination therapy in advanced DTC (and in any cancer). There is an ongoing basket trial (KEYNOTE-028 (NCT02054806)) that has enrolled patients with advanced thyroid cancer to a single agent pembrolizumab (200 mg iv every 3 weeks) study. Preliminary data from the thyroid cohort in this trial was presented at the 2016 American Society for Clinical Oncology (Mehnert JM, et al, J Clin Oncol 34, 2016 (suppl; abstr 6091)). The study enrolled 22 patients with DTC, with a median duration of follow-up of 74 weeks (29-87 weeks). No patients achieved a CR (0%) and 2 patients had a PR (9.1%), with 12 having SD (54%), which is why we will not have a pembrolizumab-only arm in this study. Our study will be done for 2 different cohorts (Cohort 1: Lenvatinib-naïve patients; Cohort 2: progressed on Lenvatinib alone). Both cohorts will receive the same combination therapy. The primary endpoint is different for the 2 cohorts, as described below (16.12 and 16.14). This study will also assess many secondary endpoints as well, as explained in detail below (16.3). Finally, this study will also assess important correlative science endpoints (16.4).
- 16.12 Overview and Primary Endpoint for Cohort 1: The complete response (CR) rate for lenvatinib alone was around 2%. The CR for patients with advanced DTC treated with pembrolizumab is 0% (see Section 16.11). A CR rate of around 15% would be clinically significant and worthy of further study. The primary endpoint for Cohort 1 is this CR rate (per RECIST 1.1 criteria). All patients meeting the eligibility criteria who have signed a consent form and have begun treatment will be considered evaluable for the primary endpoint. A patient that has a CR (Cohort 1) is considered a treatment “success”. The following one-stage binomial design (see below) requires 25 evaluable patients, and simultaneously discriminates between CR rates of 2% vs. 15%.
- 16.13 Decision Rules for Cohort 1:
- 16.131 Final Analysis Decision Rule: Enroll 25 total evaluable patients. If at least 2 patients have a success (at least 8%) among the 25 evaluable patients, this combination therapy would be considered worthy of further testing in this disease. If 0 or 1 patients have a success, this combination therapy will be considered negative and no further study would be warranted.
- 16.132 Power and Significance Level: This design has 91% power to detect a

true success rate of 15%, with a significance level of 0.09 if the true success rate is 2%.

16.14 Overview and Primary Endpoint for Cohort 2: It is expected that the confirmed response rate is around 5% in this disease population. A confirmed response rate of around 25% would be clinically significant and worthy of further study. The primary endpoint for Cohort 2 is this confirmed response rate (per RECIST 1.1 criteria). All patients meeting the eligibility criteria who have signed a consent form and have begun treatment will be considered evaluable for the primary endpoint. A confirmed tumor response is defined to be a CR or PR noted as the objective status on 2 consecutive evaluations at least 4 weeks apart. A patient that has a confirmed response (Cohort 2) is considered a treatment “success”. The following 2-stage Simon Optimal MinMax design (see below) requires a maximum of 25 evaluable patients, and simultaneously discriminates between confirmed response rates of 5% vs. 25%.

16.15 Decision Rules for Cohort 2:

16.151 Final Analysis Decision Rule: Enroll 25 evaluable patients. If at least 4 patients have a success (at least 16%) among the 25 evaluable patients, this combination therapy would be considered worthy of further testing in this disease. If 3 or fewer patients have a success, this combination therapy will be considered negative and no further study would be warranted.

16.152 Stage 1 Decision Rule: After the first 15 patients entered into the trial become evaluable for the primary endpoint, a stage 1 analysis will be performed. If 1 or more patients have a success, the study will continue to full accrual. Otherwise, if 0 successes are observed, the study will be stopped early and the treatment will be considered ineffective in this patient population. Accrual will stop after we enroll the first 15 eligible patients to this cohort.

16.153 Power and Significance Level: This design has 90% power to detect a true success rate of 25%, with a significance level of 0.05 if the true success rate is 5%.

16.16 Over Accrual: If more than the target number of patients are accrued, the additional patients will not be used to evaluate the stopping rule or used in any decision making process.

16.17 Other Considerations: Toxicity, quality/duration of response, and patterns of treatment failure observed in this study, as well as scientific discoveries or changes in standard care will be taken into account in any decision to terminate the study.

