2.0 Goals

2.1 Primary

- 2.11 To investigate the clinical efficacy, as indicated by the rate of complete response (CR) per RECIST 1.1, of combination therapy with pembrolizumab and lenvatinib in lenvatinib-naïve patients with progressive radioiodine-refractory DTC (Cohort 1).
- 2.12 To determine the overall response rate (ORR) by the addition of pembrolizumab to patients with radioiodine-refractory DTC who have progressive disease on lenvatinib alone (Cohort 2).

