11.0 Treatment Evaluation Using RECIST Guideline

NOTE: This study uses protocol RECIST v1.1 template dated 2/16/2011. See the footnote for the table regarding measurable disease in Section 11.44, as it pertains to data collection and analysis.

Response and progression will be evaluated in this study using the new international criteria proposed by the revised Response Evaluation Criteria in Solid Tumors (RECIST) guidelines (version 1.1). Changes in the largest diameter (unidimensional measurement) of the tumor lesions and the short axis measurements in the case of lymph nodes are used in the RECIST guideline.

11.1 Schedule of Evaluations: For the purposes of this study, patients should be reevaluated every 6 weeks to 18 weeks after treatment initiation, then every 12 weeks until end of active study treatment (54 weeks). In addition to a baseline scan, confirmatory scans should also be obtained at least 4 weeks following initial documentation of objective response.

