 - i. If the positive FDG-PET at follow-up corresponds to a new site of disease confirmed by CT, this is PD.
 - ii. If the positive FDG-PET at follow-up is not confirmed as a new site of disease on CT at the same evaluation, additional follow-up CT scans (i.e., additional follow-up scans at least 4 weeks later) are needed to determine if there is truly progression occurring at that site. In this situation, the date of PD will be the date of the initial abnormal PDG-PET scan.
 - iii. If the positive FDG-PET at follow-up corresponds to a pre-existing site of disease on CT that is not progressing on the basis of the anatomic images, it is not classified as PD.

11.33 Measurement at Follow-up Evaluation:

- A subsequent scan must be obtained ≥ 4 weeks following initial documentation of an objective status of either complete response (CR) or partial response (PR).
- In the case of stable disease (SD), follow-up measurements must have met the SD criteria at least once after study entry at a minimum interval of 4 weeks (see Section 11.44).
- The cytological confirmation of the neoplastic origin of any effusion that appears or worsens during treatment when the measurable tumor has met criteria for response or stable disease is mandatory to differentiate between response or stable disease (an effusion may be a side effect of the treatment) and progressive disease.
- Cytologic and histologic techniques can be used to differentiate between PR and CR in rare cases (e.g., residual lesions in tumor types such as germ cell tumors, where known residual benign tumors can remain.)

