11.43 Response Criteria

- 11.431 All target lesions and target lymph nodes followed by CT/MRI/PET-CT/Chest X-ray/physical examination must be measured on re-evaluation at evaluation times specified in Section 11.1. Specifically, a change in objective status to either a PR or CR cannot be done without re-measuring target lesions and target lymph nodes.

Note: Non-target lesions and non-target lymph nodes should be

evaluated at each assessment, especially in the case of first response or confirmation of response. In selected circumstances, certain non-target organs may be evaluated less frequently. For example, bone scans may need to be repeated only when complete response is identified in target disease or when progression in bone is suspected.

11.432 Evaluation of Target Lesions

- Complete Response (CR): All of the following must be true:
 - a. Disappearance of all target lesions.
 - b. Each target lymph node must have reduction in short axis to <1.0 cm.
- Partial Response (PR): At least a 30% decrease in PBSD (sum of the longest diameter for all target lesions plus the sum of the short axis of all the target lymph nodes at current evaluation) taking as reference the BSD (*see* Section 11.41).
- Progression (PD): At least one of the following must be true:
 - a. At least one new malignant lesion, which also includes any lymph node that was normal at baseline (< 1.0 cm short axis) and increased to ≥ 1.0 cm short axis during follow-up.
 - b. At least a 20% increase in PBSD (sum of the longest diameter for all target lesions plus the sum of the short axis of all the target lymph nodes at current evaluation) taking as reference the MSD (Section 11.41). In addition, the PBSD must also demonstrate an absolute increase of at least 0.5 cm from the MSD.
 - c. See Section 11.32 for details in regards to the requirements for PD via FDG-PET imaging.
- Stable Disease (SD): Neither sufficient shrinkage to qualify for PR, nor sufficient increase to qualify for PD taking as reference the MSD.

11.433 Evaluation of Non-Target Lesions & Non-target Lymph Nodes

- Complete Response (CR): All of the following must be true:
 - a. Disappearance of all non-target lesions.
 - b. Each non-target lymph node must have a reduction in short axis to <1.0 cm.
- Non-CR/Non-PD: Persistence of one or more non-target lesions or non-target lymph nodes.
- Progression (PD): At least one of the following must be true:

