- If at any time, 3 of the initial 10 patients (or 30% of all patients when accrual is greater than 10) have experienced any grade 4 adverse event (at least possibly related to the study medication).
 - If at any time, 1 of the initial 10 patients (or 10% of all patients when accrual is greater than 10) have experienced any grade 5 adverse event (at least possibly related to the study medication).
- 16.6 Accrual Monitoring Stopping Rule
Given the expected accrual rate is around 3 patients per month, it is expected that the study will take around 20 months to fully accrue. We plan to monitor the accrual continually and if we only end up accruing 5 patients or less in the first year (after study activation), we will consider stopping the trial for slow accrual.
- 16.7 Primary Endpoint Completion Time Estimation (For clinicaltrials.gov reporting):
The primary endpoint is the complete response (CR) rate for Cohort 1 and the confirmed response rate for Cohort 2. The final analysis is expected to take place around 36 months after the study begins, so we expect the primary endpoint completion time to be around 36 months after study activation.
- 16.8 Inclusion of Women and Minorities
- This study will be available to all eligible patients, regardless of race, gender, or ethnic origin. There is no information currently available regarding differential effects of this regimen in subsets defined by race, gender, or ethnicity, and there is no reason to expect such differences to exist. Based on prior studies involving similar disease sites, we expect about 10% of patients will be classified as minorities by race and about 50% of patients to be women. Expected sizes of racial by gender subsets are shown in the following table:

Accrual Targets			
Ethnic Category	Sex/Gender		
	Females	Males	Total
Hispanic or Latino	3	3	6
Not Hispanic or Latino	27	27	54
Ethnic Category: Total of all subjects	30	30	60
Racial Category			
American Indian or Alaskan Native	1	1	2
Asian	0	1	1
Black or African American	2	1	3
Native Hawaiian or other Pacific Islander	0	0	0
White	27	27	54
Racial Category: Total of all subjects	30	30	60

Ethnic Categories: **Hispanic or Latino** – a person of Cuban, Mexican, Puerto Rican, South or Central American, or other Spanish culture or origin, regardless of race. The term “Spanish origin” can also be used in addition to “Hispanic or Latino.”
Not Hispanic or Latino

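### Section 16.12 counts a Cohort 1 complete response seen at a single evaluation, even if the repeat scan required by Section 11 contradicts it; with a cutoff of 2 of 25, one such response can reverse the conclusion

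*Combined protocol and SAP*

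**What the plan says.** **Cohort 1.** Section 2.11 sets the goal as efficacy "as indicated by the rate of complete response (CR) per RECIST 1.1". Section 16.12 repeats it: "The primary endpoint for Cohort 1 is this CR rate (per RECIST 1.1 criteria"). The success definition follows: "A patient that has a CR (Cohort 1) is considered a treatment" success. Section 16.131 calls the combination worthy of further testing with 2 or more successes among 25 evaluable patients, and negative with 0 or 1. None of these sections mentions confirmation.

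**Cohort 2.** Section 16.14 also refers to RECIST 1.1 but adds its own rule: "A confirmed tumor response is defined to be a CR or PR noted as the objective status on 2 consecutive evaluations", with a gap of 4 weeks or more. Section 16.7 puts the two endpoints side by side: "The primary endpoint is the complete response (CR) rate for Cohort 1 and the confirmed response rate for Cohort 2".

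**Imaging, both cohorts.** Section 11.1 says that "confirmatory scans should also be obtained at least 4 weeks following initial documentation of objective response". Section 11.33 makes a later scan mandatory, at least 4 weeks "following initial documentation of an objective status of either complete response (CR) or partial response (PR"). Section 11.431 asks that non-target disease be "evaluated at each assessment, especially in the case of first response or confirmation of response". The table in 11.44 assigns objective status evaluation by evaluation.

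**The concern.** The plan obtains a second scan for every first CR in Cohort 1 but gives that scan no role in the Cohort 1 endpoint. Under the wording of 16.12, a patient with CR at one evaluation is a success whatever the repeat scan shows.

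The cutoff leaves no slack. Two CRs, one of them not confirmed, are 2/25 = 8% and positive if any CR counts, but 1/25 = 4% and negative if confirmation is required. A positive Cohort 1 result could therefore rest on a CR that the trial's own confirmatory scan did not support.

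**Working it through.** **Inputs.** n = 25, cutoff 2, null rate 2% and alternative 15% (16.12, 16.131); stated significance level 0.09 and power 91% (16.132). The share q of CRs that fail confirmation is not in the documents. I assume 10%, 20% and 30%, and add 5% as a low case.

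**1. Reproduce the stated design.** With X the number of counted CRs,

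P(X ≥ 2 | p) = 1 − (1 − p)^25 − 25p(1 − p)^24.

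- p = 0.02: 1 − 0.6035 − 0.3079 = 0.0886, which is the stated 0.09.
- p = 0.15: 0.9069, which is the stated 91%.

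Both figures are right for whichever kind of CR is counted, provided that 2% and 15% refer to that kind.

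**2. Chance that the two definitions disagree.** Let p be the any-CR rate and let each CR fail confirmation independently with probability q. The confirmed rate is then p(1 − q). Confirmed CRs are a subset of all CRs, so the definitions disagree only when any-CR is positive and confirmed-CR is negative:

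D = P(X ≥ 2 | p) − P(X ≥ 2 | p(1 − q)).

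| q (assumed) | p(1 − q) at 2% | P(X ≥ 2) | D | p(1 − q) at 15% | P(X ≥ 2) | D |
|---|---|---|---|---|---|---|
| 5% | 0.019 | 0.0812 | 0.7% | 0.1425 | 0.8896 | 1.7% |
| 10% | 0.018 | 0.0740 | 1.5% | 0.135 | 0.8695 | 3.7% |
| 20% | 0.016 | 0.0602 | 2.8% | 0.12 | 0.8195 | 8.7% |
| 30% | 0.014 | 0.0475 | 4.1% | 0.105 | 0.7544 | 15.3% |

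(D is taken from unrounded values.)

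**3. At the margin.** If exactly 2 CRs are seen, the chance that at least one fails confirmation is 1 − (1 − q)²: 19%, 36% or 51% for q = 10%, 20% or 30%.

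**4. Effect of requiring confirmation.** If 2% and 15% are confirmed-CR rates, alpha 0.0886 and power 0.907 stand. If they are any-CR rates, the P(X ≥ 2) columns give the new values: alpha 0.074, 0.060 or 0.048 and power 87%, 82% or 75% for q = 10%, 20% or 30%.

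**5. Are the scans there?** Under footnote 5 of the Section 4.0 test schedule, imaging falls on day 1 of Cycles 3, 5, 7, 11, 15 and 19. With 21-day cycles that is weeks 6, 12, 18, 30, 42 and 54, so gaps are 6 or 12 weeks. After treatment, 13.4 continues observation every 12 weeks. The next scheduled scan therefore satisfies a 4-week gap even apart from 11.33.

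**The case against.** The strongest reply is that nothing is unclear. Section 16.12 says a CR is a success; 16.14 shows that the authors define confirmation when they want it; 16.7 attaches it to Cohort 2 alone; 16.11 says that the two primary endpoints differ; and 11.44 gives CR at one evaluation. The benchmarks follow the same split: plain CR rates in 16.12, confirmed rates in 16.14.

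Most of this stands, and it rules out three stronger readings.

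- A reader might infer that the Cohort 1 definition is fully open. It is not: the text leans to any CR. The weakness is what that rule does when the mandated repeat scan disagrees.
- A reader might infer that alpha or power is misstated. If 2% were a confirmed-CR null while any CR counted, alpha would be 0.106, 0.129 or 0.159 at q = 10%, 20% or 30%. But 16.12 words the 2% as a plain CR rate, and nothing in the documents makes it a confirmed one. Nor do they say whether the 1.5% historical lenvatinib rate in Section 1.7 was confirmed.
- A reader might infer that the 16.14 definition can simply be copied. It cannot: it accepts CR or PR at both evaluations, so CR followed by PR would qualify.

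Two practical objections also stand. Under 11.44, an incompletely evaluated repeat scan turns a CR into PR or not evaluated. And patients who refuse treatment or choose alternative therapy pass to event monitoring under 13.2, whose form list in 18.1 has no RECIST measurements, so a CR first seen at their last scan could not be confirmed. The fix has to deal with both.

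The reply does not explain why a confirmatory scan is required in Cohort 1 but left without effect on a one-patient decision margin.

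**Conclusion.** The point holds as a weakness in the endpoint definition. Followed literally, the plan counts a Cohort 1 CR that the required repeat scan contradicts, and one such CR can turn a negative result into a positive one. It is not an error in the sample size, alpha or power, and Cohort 2 is unaffected.

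The size depends entirely on the assumed failure share and on independence between patients. For shares of 10% to 30%, the chance of opposite conclusions is 1.5% to 4.1% at the design null and 3.7% to 15.3% at the design alternative. The CR criteria are strict, so unconfirmed CRs may be rarer than this; at 5% the figures are 0.7% and 1.7%. The change is worth making because it is cheap and uses scans the plan already requires.

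**What to change.** In 16.12:

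- Define a Cohort 1 success as an objective status of CR at two successive evaluations separated by 4 weeks or more. This takes the timing from 16.14 but requires CR both times.
- State that a CR with no evaluable repeat scan counts as unconfirmed, including in patients who leave imaging under 13.2.
- Report unconfirmed CRs, and give the any-CR result as a sensitivity analysis.
- Have the sponsor state whether 2% and 15% are confirmed or any-CR rates. If they are any-CR rates, restate alpha and power for the confirmed endpoint, with the assumed failure share shown (step 4 of the working gives the range).

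Align 2.11, 16.131 and 16.7 with the new definition.

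**Cost.** A few sentences, with no change to n, the cutoff or the required scans. The downside is possibly lower power, and a few genuine CRs lost to incomplete repeat imaging; the any-CR sensitivity analysis keeps those visible.
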